#### *Clinical Data Collection:*

We will use electronic medical records to collect medical data from mother's antenatal, delivery and post-delivery information and detailed medical information of the infants. Data derived from blood test analysis in placenta/umbilical blood cord and blood from the infants will be used to assess the accuracy of placenta/umbilical blood cord samples. We will also find out specificity, sensitivity, positive and negative predictive values of CBC, I/T ratio, blood culture, CRP and IL-6 in the evaluation of EOS in ELBW infants. All data will be de-identified but the clinical data will be linked to the discarded samples.

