## **1. Introduction and Purpose:**

Sepsis is the leading cause of neonatal mortality and every year three million infants die worldwide due to neonatal sepsis (1). In the US, despite significant advances in care, sepsis remains a significant cause of neonatal morbidity and mortality, particularly among Very Low Birthweight (VLBW) preterm infants (PI) (2).

Neonatal early onset sepsis (EOS) is defined as onset of signs and symptoms of sepsis with positive culture <72 hours of age. Compared to term infants, the incidence of EOS is 11 times higher in preterm infants with a mortality rate ranging from 1.5% in term infants to almost 40% in VLBW preterm infants (2).

The diagnosis of neonatal sepsis is challenging, and the prognosis depends on early detection and treatment. The current “gold standard” to diagnose sepsis is a positive blood culture, but there is a variable sensitivity mostly due to inadequate sample volume, transient bacteremia, intrapartum antibiotics and administration of antibiotics before blood sample collection (3,4,5). Although the gold standard for diagnosis of bacterial sepsis is blood culture, only in 25%-40% of blood culture pathogens can be detected (6). Serum markers as IL-6 and CRP have shown to be suitable markers for detecting early onset neonatal sepsis, with a high degree of sensitivity and specificity (18).

In VLBW infants, almost 3 ml of blood is drawn to evaluate EOS for blood culture, CBC and blood group and cross match. This baseline work-up laboratory may represent almost 5-10% total blood volume of a VLBW infant. This iatrogenic acute blood loss may lead to hemodynamic instability and early red blood transfusion in the preterm infant when they are at the highest period risk for intra ventricular hemorrhage (IVH) (23).

The average infant's blood volume is 80ml/kg, while the average blood in the placenta and umbilical cord is 15 to 34 ml/kg which is discarded in the current practice (29). EOS evaluation which includes blood culture, CBC, IT ratio along with biomarkers of EOS like CRP and IL-6 could be done by using placenta/umbilical cord blood (PUCB). PUCB collection is painless, easy and adequate volume may be collected for blood culture. This procedure could decrease iatrogenic blood losses of VLBW infants (23). Currently, there is inadequate published data to support the routine use of PUCB in the evaluation of EOS in VLBW preterm infants.

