## **3. Concise Summary of Project:**

Hypothesis: Placental/umbilical cord blood can be used to do early onset sepsis evaluation in low birth weight infants.

Objective: To compare placental/umbilical cord blood and blood from the infant in the evaluation of EOS in VLBW infants.

Specific Aim 1: To compare blood culture, CBC and I/T ratio results of blood from the infant and placental/umbilical cord blood (PUCB).

Objective: All VLBW infants receive empirical broad-spectrum antibiotics after collecting blood for CBC, I/T ratio, and blood culture. We will compare the results of PUCB and blood from the infants, especially comparing white cell count, band count, I/T ratio and if the blood culture is positive or negative. If the blood culture is positive, then we will find out if the micro-organism is the same or not.

Specific Aim 2: To evaluate the role of adding IL-6 and CRP in the evaluation of EOS in VLBW infants.

Objective: We will collect 1 mL of PUCB which will be centrifuged at -40C and serum will be stored at -80 degrees. We will use ELISA to measure IL-6 and CRP. A combination of IL-6 and CRP has been shown to be very helpful in the diagnosis of EOS in VLBW infants. We will also calculate sensitivity, specificity, negative predictive and positive predictive values of IL-6 and CRP individually, as well as, a combination of IL-6 and CRP in the diagnosis of EOS in VLBW infants. We will also find out the duration of antibiotics used in all subjects and find out from IL-6 and CRP data if the antibiotic use was warranted. In future, this may be very useful information in deciding antibiotic duration which will help in avoiding side effects of the unnecessary use of broad-spectrum antibiotics. At present, in our NICU, IL-6 and CRP are not part of EOS evaluation in VLBW infants.

Clinical team will be blinded to the PUCB sepsis evaluation results. In the present study, IL-6 and CRP will not be used clinically but only for research purpose to find out if the addition of IL-6 and CRP help in the management of EOS in VLBW infants.

All VLBW infants get CBC done at admission before starting antibiotics as part of EOS work up. After CBC is done, left over blood sample is saved in the hematology laboratory for 24 hours. We will collect the left-over sample and collect serum after centrifugation. The serum will be saved at -800C for future measurement of IL-6 and CRP. We will compare IL-6 and CRP from infant and PUCB.

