#### *Placenta/Umbilical Cord blood (PUCB):*

In the current research project, we want to use PUCB to do sepsis evaluation in VLBW infants. There is approximately 15 – 20 mL/kg blood in the placenta and umbilical cord. That means in VLBW infants (<34 w) there will be approximately 15 – 20 mL blood in the placenta and umbilical cord which is fetal blood hence it can be utilized to do EOS sepsis evaluation. This

will save blood in VLBW infants. As blood in PUCB is nothing but fetal blood. There is a misconception that fetal and maternal blood is mixed in the placenta. Actually, there is no mixing of maternal and fetal blood in the placenta. After birth, the placenta and umbilical cord are discarded along with the blood inside. We want to utilize fetal blood in the placenta/umbilical cord for the evaluation of EOS in VLBW infants.

The current research project will evaluate the utility of PUCB to assess early onset sepsis (EOS) in VLBW infants (<34 weeks). This study will not affect the management of the infants at all. The lab tests will be done in blocks and hence the results will not be available in real time. The clinical management of infants will be decided by the neonatal team taking care of the infants. The neonatologists will continue to treat infants as per the NICU protocol.

We will compare blood culture, CBC, and I/T ratio results from the infant and PUCB. We will calculate the sensitivity, specificity, positive and negative predictive value of these tests in the evaluation of EOS.

During hospital stay, all VLBW infants get CBC done immediately after birth. After CBC is done, the left-over sample is stored in the hematology laboratory for 24 hours. After 24 hours, this blood sample is discarded. We will collect left over blood from the hematology laboratory to extract serum by centrifuging the blood sample. The serum will be stored at -80°C for future measurements of CRP and IL-6. We will also compare CRP and IL-6 levels in placenta/umbilical cord blood and discarded infant blood. Additionally, we will evaluate the role of adding IL-6 and CRP in the evaluation of EOS in VLBW infants.

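### Blood culture is part of the EOS definition and also a test whose accuracy for EOS is to be reported, and no independent reference standard is named

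*Combined protocol and SAP*

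**What the plan says.** Section 1 (Introduction and Purpose) holds the only definition of the disease: "Neonatal early onset sepsis (EOS) is defined as onset of signs and symptoms of sepsis with positive culture <72 hours of age". The same section says that the accepted standard to "diagnose sepsis is a positive blood culture". Neither sentence says whether the culture is from the infant, from PUCB, or from either.

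Section 3, under Placenta/Umbilical Cord blood (PUCB), states: "We will compare blood culture, CBC, and I/T ratio results from the infant and PUCB". The next sentence is: "We will calculate the sensitivity, specificity, positive and negative predictive value of these tests in the evaluation of EOS". Blood culture is one of those tests. Section 3, under Clinical Data Collection, plans "specificity, sensitivity, positive and negative predictive values of CBC, I/T ratio, blood culture, CRP and IL-6" and says that data from both specimens will be "used to assess the accuracy of placenta/umbilical blood cord samples".

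Two other parts of Section 3 bear on the reading. One says "Clinical team will be blinded to the PUCB sepsis evaluation results". The other, Specific Aim 1, plans a direct comparison of the two specimens: whether each culture is positive or negative and, if positive, whether the organism is the same.

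Section 14 (Biostatistics) uses ROC analysis to choose cord IL-6 and CRP cut-offs for EOS. It names no reference standard, no clinical or composite definition of sepsis, no adjudication, and no rule for an infant who is culture-positive in only one specimen.

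**The concern.** A test cannot be judged fairly against a definition that already contains its result; this is incorporation bias. Here every EOS case has, by definition, a positive culture, and culture is then scored for how well it finds EOS.

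The stake is the study's main question, whether PUCB can stand in for infant blood. Section 2.4 presents PUCB as a way to secure enough blood for culture. If PUCB does recover an organism that the infant sample misses, an infant-culture reference records that gain as a PUCB error. Because the reference specimen is not named, it could also be chosen after the results are known, and that choice can decide which specimen looks better.

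**Working it through.** The plan gives no expected or target accuracy for culture, so there is no figure to reproduce. The 63 infants come from a correlation calculation and are used here only as the cohort size.

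**Step 1. Infant admission culture as the reference.** EOS = signs and infant culture positive.
- Sensitivity of infant culture = P(infant culture+ | signs and infant culture+) = 1, if there is at least one case.
- NPV of infant culture = P(no EOS | infant culture−) = 1, since a culture-negative infant cannot be a case.
- Sensitivity of PUCB culture ≤ 1, so it can tie but not exceed.
- Specificity and PPV are not fixed: a culture-positive infant without signs is a false positive.

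**Step 2. Either culture as the reference.** EOS = signs and at least one positive culture. Let s_i and s_p be the true detection rates of infant and PUCB culture. Assume conditional independence given infection, no contamination, and signs in every infected infant. The share of infections that become cases is D = 1 − (1 − s_i)(1 − s_p). Apparent sensitivities are s_i/D and s_p/D.

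For s_i, the 25% and 40% in Section 1 serve as illustrative values. The documents give no s_p, so a range is assumed. For s_i = 0.25 and s_p = 0.60: D = 1 − 0.75 × 0.40 = 0.70, giving 0.25/0.70 = 36% and 0.60/0.70 = 86%. For s_i = 0.40: D = 1 − 0.60 × 0.40 = 0.76, giving 53% and 79%.

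| s_i | s_p | Infant reference: infant / PUCB sensitivity | Either reference: infant / PUCB sensitivity |
|---|---|---|---|
| 25% | 25% | 100% / 25% | 57% / 57% |
| 25% | 40% | 100% / 40% | 45% / 73% |
| 25% | 60% | 100% / 60% | 36% / 86% |
| 25% | 80% | 100% / 80% | 29% / 94% |
| 40% | 25% | 100% / 25% | 73% / 45% |
| 40% | 40% | 100% / 40% | 62.5% / 62.5% |
| 40% | 60% | 100% / 60% | 53% / 79% |
| 40% | 80% | 100% / 80% | 45% / 91% |

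In this illustration the ranking reverses wherever s_p exceeds s_i. It does not reverse in the row with 40% and 25%.

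**Step 3. Infections found only by PUCB, scored against infant culture.** Assume 10% of infants are truly infected and s_p = 0.60. PUCB-only infections are 0.10 × (1 − s_i) × 0.60 = 0.045 (s_i = 0.25) or 0.036 (s_i = 0.40). In 63 infants that is 2.8 or 2.3, all counted as PUCB false positives. Apparent PUCB specificity is 1 − 0.045/(1 − 0.025) = 95.4%, or 1 − 0.036/(1 − 0.040) = 96.3%, although no PUCB result is wrong.

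**Step 4. How many cases the 100% would rest on.** The documents give no EOS incidence for this cohort. At an assumed 1% to 5%, expected cases are 63 × 0.01 = 0.63 to 63 × 0.05 = 3.15. The chance of no case is 0.99^63 = 53% down to 0.95^63 = 4%. With 3 of 3 detected, the exact lower 95% limit is 0.025^(1/3) = 29%.

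**The case against.** The best defence is that no sentence expressly promises the sensitivity of infant culture. Clinical Data Collection can be read with PUCB as the test and infant culture as the comparator. That is a fair reading, and on it the comparison is legitimate as agreement. It does not remove the problem: the figures are still labelled as accuracy for EOS, culture is listed without a specimen, and PUCB-only infections still count as errors.

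Three stronger readings are tempting, but the documents do not support them.
- A reader might infer that infant culture scores 100% and PUCB can at best tie on any reading. This needs the infant's admission culture to be the sole reference. Blinding the clinicians to PUCB, and using infant blood as comparator, point that way, but the protocol never says so. The 100% also fails if a later culture before 72 h, or a culture of something other than blood, can make a case while only the admission blood culture is the test.
- A reader might infer that the whole culture comparison is settled by definition. Only infant sensitivity and NPV are fixed, and only under that reference. PUCB results still depend on the data, and the paired comparison in Specific Aim 1 is not circular.
- A reader might infer that infant cultures here detect only 25–40% of infections, or are handicapped by earlier antibiotics or small volume. The Section 1 sentence with those percentages is not clearly about infant-culture sensitivity. Section 3 has infant blood drawn before empirical antibiotics, and maternal intrapartum antibiotics precede both samples. Section 4 gives PUCB culture 1 mL, but the infant culture volume is not stated. A PUCB-only positive may also be contamination.

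It is also true that positive and negative percent agreement with infant culture are numerically the same as sensitivity and specificity against it. The gain is in the interpretation, not the arithmetic.

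**Conclusion.** The concern holds in conditional form. Followed as written, the plan yields a circular accuracy result for blood culture, and no section supplies an independent reference. Under the implied infant-culture reference, infant sensitivity and NPV carry no information. Under an either-specimen reference, both cultures help to define the cases on which they are scored. The reversal in the table shows that the choice of reference can matter; it does not predict this study's results, because the detection rates, independence and absence of contamination are all assumed. The culture accuracy figures should not be reported as planned. The paired data remain sound and usable.

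**What to change.** In the PUCB and Clinical Data Collection parts of Section 3, and in Section 14:

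1. State that the reference for CBC, I/T ratio, CRP and IL-6 is infant culture plus signs before 72 h. Acknowledge that it is imperfect: infections missed by infant culture will count as non-cases.
2. Remove blood culture from the tests whose sensitivity, specificity and predictive values for EOS are reported.
3. Under Specific Aim 1, report PUCB against infant culture as positive and negative percent agreement with exact confidence intervals, interpreted as agreement and not accuracy. List every discordant pair with organism, possible contamination and clinical course.
4. Treat an exact McNemar test as optional and descriptive. With all five of five discordant pairs in one direction, two-sided p = 2 × (1/2)^5 = 0.0625; six of six gives 2 × (1/2)^6 = 0.031. Fewer than six discordant pairs therefore cannot reach p < 0.05.

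The cost is wording and a small change of analysis on data already planned, with no new samples. The downside is that the study no longer reports an accuracy figure for culture itself.

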#### **4. Study Procedures:**

##### *Placenta/Umbilical cord blood (PUCB) sample collection:*

After infant is delivered, placenta along with clamped umbilical cord Blood will be obtained from the ObGyn team. One umbilical clamp will be placed at the umbilical end, and the other clamp will be placed on the placental end of the umbilical cord. Then the umbilical cord will be cut between the clamps. The umbilical cord will be cleaned three times with 2% chlorhexidine, plus 70% isopropyl alcohol under sterile conditions (sterile gloves). Cord blood samples will be collected using vacutainer blood collecting system with a sterile 22-gauge needle. We will collect 3 - 4 ml of PUCB.

##### *Discarded blood sample from infants:*

During hospital stay, all VLBW infants get CBC done immediately after birth. After CBC is done, the left-over sample is stored in the hematology laboratory for 24 hours. After 24 hours, this blood sample is discarded. We will collect left over blood from the hematology laboratory to extract serum by centrifuging the blood sample at 4°C for 10 minutes. The serum will be stored at -80°C for future measurements of CRP and IL-6.

##### *PUCB culture:*

After UCB collection, the needle will be replaced by another sterile needle and 1 ml of UCB will be transferred to the blood culture bottle. The culture bottle will be labeled with a unique identification number and immediately will be sent to the microbiology laboratory at UTMB Galveston for blood culture. On identification of positive blood culture, the blood culture bottle will be removed from the machine and will be Gram stained to make sure there are organisms seen and then sub-cultured on blood agar and Mac-Conkey agar plates. The organisms isolated on the culture plates will be identified by VITEK MS (BioMerieux).

##### *Complete blood count and I/T ratio:*

After PUCB culture, approximately 1 ml of whole blood will be transferred in an EDTA vial which will be labeled with a unique identification number. The blood sample will be sent to the hematology laboratory at UTMB Galveston for CBC and differential count. I/T ratio will be calculated from the differential count.

#### **5. Sub-Study Procedures:**

##### *IL-6 and CRP measurement:*

The remainder of the PUCB will be transferred to a heparinized container. PUCB will be centrifuged at 4°C for 10 minutes to collect supernatants (serum). Serum will be divided into aliquots of 200 microliters each and stored at -80°C for future IL-6 and CRP measurements. We will measure IL-6 by enzyme-linked immunosorbent assay (ELISA) for human IL-6.

## **6. Criteria for Inclusion of Subjects:**

**Inclusion criteria:** Subjects who will fulfil following criteria will be included in the study -

1. Infants < 34 weeks' gestational age, born at UTMB, Galveston

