The purpose of the present study is to evaluate the utility of placenta/umbilical cord blood (PUCB) to perform the baseline workup testing (CBC, I/T ratio, blood culture) along with CRP and IL-6 levels in the evaluation of EOS in VLBW infants.

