## 2.2 *IL-6*

IL-6 is a pro-inflammatory cytokine produced by mononuclear phagocytes, endothelial cells, and fibroblasts in response to inflammation. IL-6 levels peaks 2-3 hours after inflammatory

responses, and returns to baseline after 6 to 8 hours (16). IL-6 is the primary inducer of hepatic acute-phase protein synthesis, including CRP and fibrinogen (17). IL-6 levels are not influenced by gestational age and has been shown to have high sensitivity in diagnosing EOS (16,18).

Messer et al. in a prospective study, measured IL-6 levels (n=157) upon admission to the NICU and the in umbilical cord blood (n=131) (18). The sensitivity and NPV of IL-6 in the diagnosis of blood culture positive and clinical sepsis was 100% in those infants who had an early measurement of IL-6 at birth (umbilical cord blood) or blood drawn from the infant within one hour after birth. Moreover, they found high sensitivity and NPV persisted until the twelfth hour of age. Krueger et al. found umbilical cord blood IL-6 levels have high sensitivity (87%) and specificity (90%) in 71 term and 100 preterm infants. When only preterm infants were included in the analysis, IL-6 sensitivity and specificity increased to 96% and 94% (19).

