### *2.4 Reducing blood withdrawals in preterm infants*

Placental/umbilical cord blood (PUCB) could be used in the evaluation of EOS in PI. (23,26). Christensen found reduced iatrogenic blood loss using PUCB sample during the first day of life ( $p < 0.007$ ), and for the first week of life ( $p < 0.001$ ) in contrast with infant blood sample controls (23). This postpone or eliminating blood transfusion in the VLBW preterm infant (23,26).

PUCB for blood cultures could be a convenient alternative to ensure an adequate volume of blood (24). Meena et al. compared PUCB with blood from infants, (n=40) in the evaluation of sepsis. They found PUCB showed 100% sensitivity and 95% of specificity compared with 100% of sensitivity and 74% of specificity using blood from infants. Beeram et al found that the utilization of umbilical blood samples for CBC and blood cultures are a reliable alternative for sepsis workup in neonates (25).

In the current study, we want to find out the efficacy of PUCB in the evaluation of EOS in preterm infants compared to blood collected from the infant (24).

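### Accuracy is promised for VLBW or ELBW infants, but the cohort is selected only on gestation below 34 weeks, so it may be broader than the label on its results

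*Combined protocol and SAP*

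**What the plan says.** Eligibility rests on gestation and place of birth alone: "Infants < 34 weeks' gestational age, born at UTMB, Galveston" (section 6). The three exclusions in section 7 concern anomalies, heart disease and multiple pregnancy. None concerns weight.

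The population named for the question and the results varies:

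- Purpose (section 1): "along with CRP and IL-6 levels in the evaluation of EOS in VLBW infants".
- Hypothesis (section 3): "Placental/umbilical cord blood can be used to do early onset sepsis evaluation in low birth weight infants".
- Objective (section 3): "To compare placental/umbilical cord blood and blood from the infant in the evaluation of EOS in VLBW infants".
- Aim 2 (section 3), which promises sensitivity, specificity and predictive values for IL-6 and CRP singly and for "a combination of IL-6 and CRP in the diagnosis of EOS in VLBW infants".
- Clinical Data Collection (section 3): the same accuracy measures, with those of CBC, I/T ratio and culture, for ELBW infants.
- Potential Benefits (section 13): VLBW infants, with ELBW in the sentence on antibiotic use.

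Elsewhere the cohort is described by maturity. Section 2.4 sets out to study "the efficacy of PUCB in the evaluation of EOS in preterm infants compared to blood collected from the infant". The power analysis in section 3 refers to preterm infants, and the part of section 3 on placental/umbilical cord blood twice puts a 34-week limit in brackets after VLBW. Section 1 expands the abbreviation as a weight term: "particularly among Very Low Birthweight (VLBW) preterm infants (PI").

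**The concern.** One cohort, defined by gestation, carries three birth-weight labels. A gestation limit does not cap birth weight, so an infant below 34 weeks who is not of very low birth weight is eligible and would contribute to figures reported under a VLBW or ELBW heading.

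At stake is what the trial may claim from Aim 2 and the other accuracy measures. Predictive values depend on how common EOS is in the infants studied, and sensitivity and specificity can vary with case mix. A reader who applies published values to VLBW or ELBW infants needs to know that they came from such infants. Section 14 plans adjustment for gestational age but no analysis by birth weight. That adjustment does not turn an estimate from the whole cohort into a VLBW estimate.

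**Working it through.** **1. The plan's own accrual figure.** Inputs, from the power analysis in section 3 and from section 9: about 80 admissions a year below 34 weeks; recruitment of 50-60%; 18 months; target 63.

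- Admissions in 18 months: 80 x 1.5 = 120.
- Expected recruits: 120 x 0.50 = 60 to 120 x 0.60 = 72.
- Recruitment fraction needed: 63 / 120 = 52.5%.

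The target lies inside 60-72, so the forecast is reproduced, but only when every admission below 34 weeks is counted. The two sections then attach the 50-60% to different groups: the power analysis to VLBW infants, section 9 to all eligible infants. These agree only if VLBW is simply another name for below 34 weeks.

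**2. Can that equation hold throughout?**

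| Place | Label | Explained by a 34-week gloss? |
|---|---|---|
| Section 1, purpose | VLBW | Only if the weight expansion in the same section is set aside |
| Section 3, hypothesis | Low birth weight | No |
| Section 3, objective and Aim 2 | VLBW | As for the purpose |
| Section 3, Clinical Data Collection | ELBW | No |
| Section 13 | VLBW and ELBW | VLBW as above; ELBW no |
| Section 6 | Below 34 weeks | This is the rule itself |

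The gloss settles who is enrolled. It does not make a gestation cut-off a weight category, and it cannot account for the other two labels. Aim 2 and Clinical Data Collection give the same IL-6 and CRP accuracy measures two different population names.

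**3. What is affected.** The comparison of cord and infant blood is made within each infant, so the label does not bias it. The sample size of 63 is derived from a correlation of 0.4 and has no weight input. Only the population to which the accuracy estimates are attached is affected.

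**4. How large?** If v is the share of enrolled infants who are VLBW, the VLBW subset has 63 x v infants. The documents give neither v nor a gram threshold. Under assumed shares, for illustration only:

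- v = 75%: 63 x 0.75 = 47.25, about 47
- v = 50%: 63 x 0.50 = 31.5, about 32
- v = 25%: 63 x 0.25 = 15.75, about 16

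**The case against.** The best defence is that this is loose terminology. Section 3 equates VLBW with the eligibility rule, sections 3 and 9 count admissions by gestation, and enrolment, sampling and the paired comparison would not change. The ELBW wording in Clinical Data Collection looks like a drafting slip, and that in section 13 concerns future benefit. Section 3 also converts 15-20 mL/kg of placental blood into 15-20 mL, which implies infants of about 1 kg (15/15 = 20/20 = 1), so the authors evidently have small infants in mind.

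Most of this stands: who is enrolled is not in doubt, and the paired comparison is sound. But picturing infants of 1 kg is not selecting on weight, and the accuracy measures are still promised under weight labels.

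Four stronger readings are tempting, and the documents do not support them.

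- *The results would describe the wrong population.* With no weight distribution, the text supports only a cohort possibly broader than the label.
- *Section 2.2 shows that accuracy would shift.* It says of one cited study of 71 term and 100 preterm infants: "When only preterm infants were included in the analysis, IL-6 sensitivity and specificity increased to 96% and 94" per cent, from 87% and 90%. That change comes from dropping term infants, whom section 6 already excludes, and it is a contrast of maturity. The statements in sections 2.1 and 2.2 that CRP and IL-6 levels do not depend on gestational age do not settle the matter either: they concern levels, not accuracy, and not weight. No section says how accuracy varies with birth weight.
- *A weight restriction is what puts 63 out of reach at 50% recruitment.* The gestation count alone gives 60 at 50%, already below 63.
- *Enrolment would run far past 18 months.* That would be the cost of a weight-selected cohort, which the plan does not propose, and not a harm of the plan as written.

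**Conclusion.** The inconsistency is certain from the text: selection is on gestation, while the accuracy results are labelled by birth weight in two different ways and the hypothesis uses a third weight term. Followed as written, the plan would attach sensitivity, specificity, PPV and NPV to a weight-defined population that it did not select. The effect is limited to what may be concluded and for whom. The size of the mismatch is unknown, and the subset sizes shown above rest wholly on assumed shares. The point should be corrected, but it does not undermine the design.

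**What to change.** Use one population, infants below 34 weeks' gestation, in the hypothesis, objectives, aims, accrual text, data-collection text and conclusions. This matches section 6, section 9 and the admission count in the power analysis. In the power analysis, apply the 50-60% to eligible infants, as section 9 does.

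If the sponsor wants any VLBW or ELBW statement, pre-specify that subset in section 14 with a stated birth-weight limit, take birth weight from the medical record (the data source already named in Clinical Data Collection), and report its n beside its accuracy estimates with confidence intervals.

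The cost is a wording change, plus one subset table only if a weight-specific claim is kept. The target of 63 and the procedures stay as they are. The downside is that a weight-specific claim would rest on fewer than 63 infants, by an amount the documents do not allow one to predict, and so on less precise estimates.
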